11.1.5 Unanticipated Problems

Definition:

- unexpected (in terms of nature, severity, or frequency) given (a) the research procedures that are described in the protocol-related documents, such as the IRB-approved research protocol and informed consent document; and (b) the characteristics of the subject population being studied;
- related or possibly related to participation in the research (“possibly related” means there is a reasonable possibility that the incident, experience, or outcome may have been caused by the procedures involved in the research); and
- suggests that the research places subjects or others at a greater risk of harm (including physical, psychological, economic, or social harm) than was previously known or recognized.

11.1.6 Noncompliance

Definition: failure to follow any applicable regulation or institutional policies that govern human subjects research or failure to follow the determinations of the IRB. Noncompliance may occur due to lack of knowledge or due to deliberate choice to ignore regulations, institutional policies, or determinations of the IRB.

11.1.7 Serious Noncompliance

Definition: noncompliance that materially increases risks, that results in substantial harm to subjects or others, or that materially compromises the rights or welfare of participants.

11.1.8 Protocol Exceptions

Definition: A planned deviation from the approved protocol that are under the research team’s control. Exceptions apply only to a single participant or a singular situation.

Local IRB Pre-approval of all protocol exceptions must be obtained prior to the event. For secondary sites, the Washington University PI will issue approval of the exception, but it must also be submitted to the local IRB with documentation of approval forwarded to Washington University. Washington University IRB approval is not required for protocol exceptions occurring at secondary sites.

11.2 Product Complaints

Definition: A product complaint is a verbal, written, or electronic expression that implies dissatisfaction regarding the identity, strength, purity, quality, or stability of a drug product. Individuals who identify a potential product complaint situation should immediately contact MedComm Solutions (see below) and report the event. Whenever possible, the associated product should be maintained in accordance with the label instructions pending further guidance from a Millennium Quality representative.

Product complaints in and of themselves are not AEs. If a product complaint results in an SAE, an SAE form should be completed (refer to Section 8.10).

11.3 Medication Error

A medication error is a preventable event that involves an identifiable patient and that leads to inappropriate medication use, which may result in patient harm. While overdoses and underdoses constitute medication errors, doses missed inadvertently by a patient do not. Individuals who identify a potential medication error situation should immediately contact Millennium (see below) and report the event

11.4 Reporting to the Human Research Protection Office (HRPO) at Washington University

The PI is required to promptly notify the IRB of the following events:

- Any unanticipated problems involving risks to participants or others which occur at WU, any BJH or SLCH institution, or that impacts participants or the conduct of the study.
- Noncompliance with federal regulations or the requirements or determinations of the IRB.
- Receipt of new information that may impact the willingness of participants to participate or continue participation in the research study.

These events must be reported to the IRB within **10 working days** of the occurrence of the event or notification to the PI of the event. The death of a research participant that qualifies as a reportable event should be reported within **1 working day** of the occurrence of the event or notification to the PI of the event.

11.5 Reporting to the Quality Assurance and Safety Monitoring Committee (QASMC) at Washington University

The PI is required to notify the QASMC of any unanticipated problem occurring at WU or any BJH or SLCH institution that has been reported to and acknowledged by HRPO as reportable. (Unanticipated problems reported to HRPO and withdrawn during the review process need not be reported to QASMC.)

QASMC must be notified within 10 days of receipt of IRB acknowledgment via email to a QASMC auditor.

11.6 Reporting Requirements for Secondary Sites

The research team at each secondary site is required to promptly notify the Washington University PI and research coordinator of all reportable events (as described in Section 11.7) within **1 working day** of the occurrence of the event or notification of the secondary site's PI of the event. This notification may take place via email if there is not yet enough information for a formal written report (using either an FDA MedWatch form if required or an institutional SAE reporting form if not). A formal written report must be sent to the Washington University PI and research coordinator within **10 working days** of the occurrence of the event or notification of the secondary site's PI of the event. The death of a research participant that qualifies as a reportable event should be reported within **1 working day** of the occurrence of the event or notification of the secondary site's PI of the event.

The research team at a secondary site is responsible for following its site's guidelines for reporting applicable events to its site's IRB according to its own institutional guidelines. The research team at Washington University is responsible for reporting all applicable events to the FDA.

11.7 Reporting to Secondary Sites

The Washington University PI (or designee) will notify the research team at each secondary site of all reportable events that have occurred at other sites within **10 working days** of the occurrence of the event or notification of the PI of the event. This includes events that take place both at Washington University and at other secondary sites, if applicable.

11.8 Reporting to the FDA

The conduct of the study will comply with all FDA safety reporting requirements. **PLEASE NOTE THAT REPORTING REQUIREMENTS FOR THE FDA DIFFER FROM REPORTING REQUIREMENTS FOR HRPO/QASMC.** It is the responsibility of the Washington University principal investigator to report any unanticipated problem to the FDA as follows:

- Report any unexpected fatal or life-threatening adverse experiences (Section 11.1.4) associated with use of the drug by telephone or fax no later than **7 calendar days** after initial receipt of the information.
- Report any serious, unexpected adverse experiences (Section 11.1.2), as well as results from animal studies that suggest significant clinical risk within **15 calendar days** after initial receipt of this information.

All MedWatch forms will be sent by the investigator or investigator's team to the FDA at the following address or by fax:

Food and Drug Administration
 Center for Drug Evaluation and Research
 Division of Oncology Drug Products
 [name]
 [name]
 FAX: [name]

Secondary sites must submit a completed MedWatch form to the Washington University PI and research coordinator within **4 calendar days** (for fatal or life-threatening adverse experiences) or **11 calendar days** (for serious, unexpected adverse experiences). The Washington University PI will be responsible for submitting all MedWatch forms from secondary sites to the FDA within the timeframes specified above.

11.9 Reporting to Millennium

AEs may be spontaneously reported by the patient and/or in response to an open question from study personnel or revealed by observation, physical examination, or other diagnostic procedures. Any clinically relevant deterioration in laboratory assessments or other clinical finding is considered an AE. When possible, signs and symptoms indicating a common underlying pathology should be noted as one comprehensive event. For serious AEs, the investigator must determine both the intensity of the event and the relationship of the event to study drug administration.

AEs which are serious must be reported to Millennium Pharmacovigilance (or designee) from the first dose of study drug through 30 days after administration of the last dose of ixazomib. Any SAE that occurs at any time after completion of ixazomib treatment or after the designated follow-up period that the sponsor-investigator and/or sub-investigator considers to be related to any study drug must be reported to Millennium Pharmacovigilance (or designee). In addition, new primary malignancies that occur during the follow-up periods must be reported, regardless of causality to study regimen, for a minimum of three years after the last dose of the investigational product, starting from the first dose of study drug. All new cases of primary malignancy must be reported to Millennium Pharmacovigilance (or designee).

Regardless of expectedness or causality, all SAEs (including serious pretreatment events) must also be reported in English to Millennium Pharmacovigilance (or designee). Fatal

and life threatening SAEs must be reported within 24 hours of the sponsor-investigator's observation or awareness of the event, and all other serious (non-fatal/non life threatening) events must be reported within 4 calendar days of the sponsor-investigator's observation or awareness of the event.

US and Canada
Toll-Free [contact]
E-mail: [contact]

If a woman becomes pregnant or suspects that she is pregnant while participating in this study, she must inform the investigator immediately and must permanently discontinue bortezomib. A Pregnancy Form must be requested, completed, and faxed to Millennium Pharmacovigilance. The pregnancy must be followed for the final pregnancy outcome.

If a female partner of a male patient becomes pregnant during the male patient's participation in this study, this must be reported to Millennium Pharmacovigilance immediately using the Pregnancy Form. Every effort should be made to follow the pregnancy for the final pregnancy outcome.

11.10 Timeframe for Reporting Required Events

Adverse events will be collected from first dose of study treatment through the end of study visit.

12.0 MEASUREMENT OF EFFECT

12.1 Response Criteria

Response will be determined by the International Myeloma Working Group (IMWG) Uniform Response Criteria.³⁶

12.1.1 Stringent Complete Response

Stringent complete response (sCR) requires all of the following:

- CR as defined below
- Normal free light chain ratio (0.26-1.65)
- Absence of clonal cells in the bone marrow by immunohistochemistry or immunofluorescence

12.1.2 Complete Response

Complete response (CR) requires all of the following:

- Disappearance of monoclonal protein by both protein electrophoresis and immunofixation studies from the blood and urine
- If serum and urine monoclonal protein are unmeasurable, Normal free light chain ratio (0.26-1.65)
- <5% plasma cells in the bone marrow
- Disappearance of soft tissue plasmacytoma

12.1.3 Very Good Partial Response

Very good partial response (VGPR) requires all of the following:

- Serum and urine monoclonal protein detectable by immunofixation but not on electrophoresis
OR
 $\geq 90\%$ reduction in serum monoclonal protein with urine monoclonal protein < 100 mg per 24 hours
- If serum and urine monoclonal protein are unmeasurable, a $\geq 90\%$ decrease in difference between the involved and uninvolved free light chain levels is required in place of monoclonal protein criteria (The absolute decrease must be > 10 mg/dl)
- If present, > 50% reduction in the size of soft tissue plasmacytomas (by clinical or radiographic examinations)

12.1.4 Partial Response

Partial response (PR) requires all of the following:

- $\geq 50\%$ reduction in the level of the serum monoclonal protein
- Reduction in urine monoclonal protein by either $\geq 90\%$ or to < 200 mg
- If serum and urine monoclonal protein are unmeasurable, a $\geq 50\%$ decrease in difference between the involved and uninvolved free light chain levels is required in place of monoclonal protein criteria (The absolute decrease must be > 10 mg/dl)
- If serum and urine monoclonal protein are unmeasurable and serum free light chain is unmeasurable, a $\geq 50\%$ reduction in plasma cells is required in place of monoclonal protein, provided that baseline bone marrow plasma cell percentage was $\geq 30\%$
- If present, > 50% reduction in the size of soft tissue plasmacytomas (by clinical or radiographic examinations).

12.1.5 Stable Disease

Stable disease (SD) is defined as not meeting criteria for any other response as defined in this section.

12.1.6 Progressive Disease or Clinical Relapse

Progressive disease (PD) requires one or more of the following:

- $\geq 25\%$ increase in the level of serum monoclonal protein, which must also be an absolute increase of at least 0.5 g/dL and confirmed on a repeat investigation
- $\geq 25\%$ increase in 24-hour urine monoclonal protein, which must also be an absolute increase of at least 200 mg/24hr and confirmed on a repeat investigation.
- If serum and urine monoclonal protein are unmeasurable, $\geq 25\%$ increase in the difference between involved and uninvolved free light chain levels, which must also be an absolute increase of at least 10 mg/dL and confirmed on a repeat investigation
- $\geq 25\%$ increase in plasma cells in a bone marrow aspirate or on trephine biopsy, which must also be an absolute increase of at least 10%.
- Definite increase in the size of existing lytic bone lesions or soft tissue plasmacytomas. A definite increase is defined as at least 50% (and at least 1 cm) increase as measured serially as the sum of the products of the cross-diameters of the lesions.
- Development of new bone lesions or soft tissue plasmacytomas (not including compression fracture).
- Development of hypercalcaemia (corrected serum calcium > 11.5 mg/dL or 2.8 mmol/L not attributable to any cause other than progressive multiple myeloma).
- Decrease in hemoglobin > 2 g/dl not attributable to any cause other than progressive multiple myeloma
- Increase in creatinine by > 2 mg/dl not attributable to any cause other than progressive multiple myeloma
- Other worsening laboratory result, or clinical condition that the treating physician determines is not attributable to any cause other than progressive multiple myeloma

Note: A response of progressive disease/clinical relapse nullifies any other concurrent response. For example, at a given time point a participant meets criteria for VGPR but has development of new bone lesions the response is PD not VGPR.

12.1.7 Relapse from Complete Response

Relapse from a complete response requires a prior CR or sCR as described above and subsequently developing one or more of the following:

- Reappearance of serum or urinary paraprotein on immunofixation or routine electrophoresis excluding oligoclonal immune reconstitution, and confirmed on a repeat investigation
- Development of $\geq 5\%$ plasma cells in the bone marrow aspirate or biopsy.
- Appearance of any sign of progressive disease or clinical relapse as stated above.

12.2 Minimal Residual Disease

For the purposes of this study, a patient will be considered as having minimal residual diseases if a positive result is obtained using the Adaptive Clonoseq MRD testing. In the event that Adaptive Clonoseq cannot be performed, a patient will be considered as having minimal residual diseases if a positive result is obtained using the Mayo MFC MRD Panel.

13.0 DATA AND SAFETY MONITORING

In compliance with the Washington University Institutional Data and Safety Monitoring Plan, the Data and Safety Monitoring Committee (DSMC) will meet to review toxicity data at least every 6 months following the activation of the first secondary site. The report will be prepared by the statistician with assistance from the study team and will be submitted to the Quality Assurance and Safety Monitoring Committee (QASMC). This report will include:

- HRPO protocol number, protocol title, Principal Investigator name, data coordinator name, regulatory coordinator name, and statistician
- Date of initial HRPO approval, date of most recent consent HRPO approval/revision, date of HRPO expiration, date of most recent QA audit, study status, and phase of study
- History of study including summary of substantive amendments; summary of accrual suspensions including start/stop dates and reason; and summary of protocol exceptions, error, or breach of confidentiality including start/stop dates and reason
- Study-wide target accrual and study-wide actual accrual including numbers from participating sites
- Protocol activation date at each participating site
- Average rate of accrual observed in year 1, year 2, and subsequent years at each participating site
- Expected accrual end date, accrual by site, and accrual by cohort
- Objectives of protocol with supporting data and list the number of participants who have met each objective
- Measures of efficacy

- Early stopping rules with supporting data and list the number of participants who have met the early stopping rules
- Summary of toxicities at all participating sites and separated by cohorts with the number of dose-limiting toxicities indicated
- Abstract submissions/publications
- Summary of any recent literature that may affect the safety or ethics of the study

Until such a time as the first secondary site activates this protocol, a semi-annual DSM report to be prepared by the study team will be submitted to the QASM Committee beginning 6 months after study activation at Washington University.

The study principal investigator and Research Patient Coordinator will monitor for serious toxicities on an ongoing basis. Once the principal investigator or Research Patient Coordinator becomes aware of an adverse event, the AE will be reported to the HRPO and QASMC according to institutional guidelines.

A DSMC will consist of no fewer than 3 members including 2 clinical investigators and a biostatistician. Like investigators, DSMC members are subject to the Washington University School of Medicine policies regarding standards of conduct. Individuals invited to serve on the DSMC will disclose any potential conflicts of interest to the trial principal investigator and/or appropriate university officials, in accordance with institution policies. Potential conflicts that develop during a trial or a member's tenure on a DSMC must also be disclosed.

Refer to the Washington University Quality Assurance and Data Safety Monitoring Committee Policies and Procedures for full details on the responsibilities of the DSMC at <https://siteman.wustl.edu/wp-content/uploads/2015/10/QASMC-Policies-and-Procedures-03.31.2015.pdf>

14.0 AUDITING

Since Washington University is the coordinating center, each site will be audited annually by Siteman Cancer Center personnel (QASMC) unless the outside institution has an auditing mechanism in place and can provide a report. The outside sites will be asked to send copies of all audit materials, including source documentation. The audit notification will be sent to the Washington University Research Patient Coordinator, who will obtain the audit materials from the participating institution.

Notification of an upcoming audit will be sent to the research team one month ahead of the audit. Once accrual numbers are confirmed, and approximately 30 days prior to the audit, a list of the cases selected for review (up to 10 for each site) will be sent to the research team. However, if during the audit the need arises to review cases not initially selected, the research team will be asked to provide the additional charts within two working days.

Additional details regarding the Auditing Policies and procedures can be found at http://www.siteman.wustl.edu/uploadedFiles/Research_Programs/Clinical_Research_Resources/Protocol_Review_and_Monitoring_Committee/QASMCQualityAssurance.pdf

15.0 STATISTICAL CONSIDERATIONS

This is an open-label, randomized phase II study that will accrue at 4-6 centers within the United States. The total accrual goal is 220 patients evaluable for the primary objective. We estimate the percentage of patients treated that will be evaluable for the primary objective to be > 90%, thus a total accrual of up to ~240 patients may be needed. The estimated accrual is 10-12 patients per month, with a projected enrollment time frame of 24 months.

[figure not shown]
15.1 Determination of Sample Size

A power analysis was performed for the primary objective. The smallest increase in MRD-negative rate after four cycles of IRD that would warrant further investigation is 10%, with a result of $\leq 9\%$ being considered ineffective. Based on a meta-analysis of five prior studies in this population, the expected MRD-negative rate at Day 100 post-transplant is ~50%. If the true rate of MRD-negative is 40-60% at the Day 100 post-transplant visit, 220 evaluable patients will detect a 10% improvement in MRD-negative rate with 90% power at 1-sided 0.05 alpha. Due to highly varied data of baseline MRD (i.e., 5 published studies showed MRD-negative rates ranged from 8% to 62%) as well as the lack of pilot information for the association over time, we currently choose a rather conservative estimation and the sample size is estimated using non-paired design instead. However, an interim analysis will be performed when ~50 patients are randomized to maintenance arms, and sample size adjustment will then be made if needed (see details below for interim analysis).

The randomized maintenance portion of the study will provide pilot data that will be used to design future studies. Although the study was not powered to show non-inferiority or superiority of either of the two maintenance arms, the designed sample size (n=110 evaluable patients/arm) will provide us a reasonable power for our hypothesis that "Maintenance therapy with ixazomib will be well tolerated and will be similar in response rate, PFS, OS, and MRD-positive to MRD-negative conversion rate to maintenance therapy with lenalidomide". Taking PFS as an example, the recent meta-analysis of lenalidomide versus placebo/observation showed that the 5-year cumulative incidence of events (PD or 2nd-line treatment) was ~54%. [29] The figure below illustrates the statistical power to show non-inferiority given the "true" difference of event rates (e.g., death or recurrence or treatment failure) between the ixazomib arm (experimental group) and lenalidomide arm (control group). With a non-inferiority margin of 10% in 5-year PFS (or equivalently a hazard ratio (HR) of 1.3), for example, the designed sample size would allow 80% power to claim non-inferiority when a slightly better PFS is observed in the ixazomib arm.

This power analysis was based on a simulation study where

- the true rate in the experimental treatment (ixazomib) varied from 45% to 65%;
- the true recurrence rate in the control (lenalidomide) varied from 52% to 56%;
- a total of 10,000 replicates are generated under each scenario, and each replicate includes N=110 ixazomib patients and N=110 lenalidomide patients;
- events in each arm were generated following binomial distributions;
- 1-sided 90% confidence interval (CI) for the difference between event rates was calculated and non-inferiority will be declared if the upper boundary of CI is below 10% [30]. That is, the non-inferiority margin was set as 10% absolute difference, or equivalently a hazard ratio (HR) of 1.3 when assuming the time following an exponential distribution;
- The figure shows average power as a function of the true difference of event rates between experimental and control groups;
- Note that the current simulation was based on binary data for simplicity. We expect that more power could be achieved in the actual time-to-event analysis due to the availability of richer information (i.e., not only the status of event, but also the exact time when it happens).

The accrual rate over six participating centers will be roughly 6 patients per month, with a total accrual timeframe of about 3 years following study activation.

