1.4.1 Hypotheses

- Consolidation with 4 cycles of IRD will be well tolerated and will result in \geq 15% improvement in MRD-negative rate
- MRD-negativity after 4 cycles of IRD consolidation will be associated with an improved PFS and OS
- Maintenance therapy with ixazomib will be well tolerated and will be similar in response rate, PFS, OS, and MRD-positive to MRD-negative conversion rate to maintenance therapy with lenalidomide.

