15.3 Data Analysis

For the analysis of consolidation therapy, the data for safety analysis will include these patients who have at least 1 dose of IRD consolidation therapy, while the data for efficacy analysis will include patients who complete 4 cycles therapy. Demographic and clinical characteristics of the sample, as well as adverse events, complications and loss to follow-up will be summarized using descriptive statistics. The change of MRD-negative rates for pre- and post-consolidation therapy will be described using contingency table and compared by McNemar test. The incidences of mortality, progression, relapse, as well as tumor response (complete response and overall) and their 95% confidence intervals following consolidation therapy will also be calculated.

Data analysis for maintenance portion will be performed following the intent-to-treat (ITT) principle. The balance of demographic and baseline clinical characteristics between two arms will be compared using t-test, Mann-Whitney rank-sum test, or Chi-square test as appropriate. The distributions of responses and adverse events across two arms will be summarized using contingency tables and compared by 2-sample Chi-square test or Fisher's exact test. Contingency table and Fisher's exact test will also be used to assess the between-arms difference for the rates of conversion from MRD-positive to MRD-negative. Chi-square test will be used to compare the distribution of responses, and Kaplan-Meier curves with log rank tests will be used to compare PFS and OS.

Overall survival (OS) will be defined as time from ASCT to death due to any causes, and survivors will be censored at withdrawal or study closeout. Progression-free survival (PFS) will be defined as time from ASCT to progression, relapse, or death, whichever occurs first, and those event-free survivors will be censored at withdrawal or study closeout. The between-arm differences in OS and PFS will be described using Kaplan-Meier product limit estimator and compared by log-rank tests. Kaplan-Meier curves will also be used to describe the association between MRD status (both prior to and after consolidation therapy) and OS or PFS, and proportional hazards Cox models will be used to control the potential confounding effects of other patient and clinical characteristics.

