15.4 Interim Analysis

Two interim analyses will be performed during the consolidation phase of the trial. The first will occur when ~50 patients complete the consolidation therapy and are randomized to maintenance portion. The second will occur in Year-3, after approximately 150 evaluable patients complete the consolidation therapy and are randomized to maintenance portion.

The data analysis will be descriptive in nature. The change of MRD-negative rates for pre- and post-consolidation therapy will be estimated using contingency table. Sample size will be re-estimated and conditional power will also be calculated based on the accumulated data. Conditional power is defined as the projected power to reject the null hypothesis at the end of study given the data accrued up to a specific interim analysis.

Therefore, a high value of conditional power indicates a highly likely, if not inevitable, conclusion to reject the null hypothesis given the available information. Similarly, a small value suggests a high possibility of negative finding given the current data. This interim analysis will assist investigators on the decision whether the sample size (220 evaluable, ~240 total) needs to be adjusted.

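### The stated 90% power with 220 patients holds for the planned McNemar test only if about 26% or fewer patients change MRD status, so the claim of conservative sizing is unsupported

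*Combined protocol and SAP*

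**What the plan says.** Section 15.1 sizes the trial on the primary objective: "220 evaluable patients will detect a 10% improvement in MRD-negative rate with 90% power at 1-sided 0.05 alpha". The condition attached is on the baseline: "If the true rate of MRD-negative is 40-60% at the Day 100 post-transplant visit". The section gives the variability of published baseline rates (8% to 62%) and the "lack of pilot information for the association over time" as reasons for its method, and concludes that "we currently choose a rather conservative estimation and the sample size is estimated using non-paired design instead". It does not name the formula.

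Section 15.3 sets the primary analysis: "The change of MRD-negative rates for pre- and post-consolidation therapy will be described using contingency table and compared by McNemar test". It restricts the population: "the data for efficacy analysis will include patients who complete 4 cycles therapy". It does not repeat the sidedness or say which version of the McNemar test is meant.

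Section 15.4 plans looks at about 50 and about 150 patients, at which "Sample size will be re-estimated and conditional power will also be calculated based on the accumulated data". No section gives a value for pre/post discordance or correlation.

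**The concern.** Each patient is measured before and after consolidation and the test is paired. For a given net gain and number of patients, McNemar power falls as discordance rises. A 90% figure conditioned on the baseline rate alone therefore leaves out the quantity that governs the power.

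Calling the sizing conservative tells the reader that the paired test will do at least as well. That would be a fair description of a calculation treating the two time points as independent samples, provided the true association is positive. It is not a property of every non-paired calculation. The 90% supports the primary-endpoint sample size of 220 evaluable patients (about 240 in total), so it matters which calculation stands behind it.

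**Working it through.** **Inputs from the documents.** n = 220 evaluable; gain d = 0.10; 1-sided alpha 0.05 (z = 1.645); baseline p0 = 0.40 to 0.60, so p1 = p0 + 0.10 (all 15.1); McNemar test (15.3).

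**Assumption.** The documents give no discordant proportion pd, so a range is shown. The lowest possible value for a 10-point gain is 10%, where power is near 100%. No pre/post association gives pd = p0(1 − p1) + p1(1 − p0), which is 50%, 50% and 46% at p0 = 40%, 50% and 60%.

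**Step 1: reproduce the stated 90%.**

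- *One-sample exact binomial test of the post-consolidation rate against a known p0.* The critical counts are 101, 123 and 145 of 220 at p0 = 40%, 50% and 60% (actual alpha 0.043, 0.046, 0.042). Power is 90.0%, 90.4% and 91.8%. This matches the plan.
- *Two independent samples of 220, pooled-variance formula.* At p0 = 50%: 0.10√220 = 1.483; 1.645 × √(2 × 0.55 × 0.45) = 1.157; (1.483 − 1.157)/√(0.25 + 0.24) = 0.466, so power is 67.9%. At 40% and 60% it is 67.9% and 71.1%. Reaching 90% needs 423, 423 and 388 per time point at the three baselines.

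Of these, only the calculation that ignores sampling error in the baseline gives 90%. At p0 = 50% its normal-approximation form is Φ((0.10√220 − 1.645√0.25)/√0.24) = 91.1%. This is term for term the McNemar formula below with pd = 0.25, since 0.25 − 0.10² = 0.24. At that baseline, the fixed-baseline formula therefore gives the paired test's power at 25% discordance.

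**Step 2: power of the planned test.**

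Power = Φ( (d√n − 1.645√pd) / √(pd − d²) )

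At pd = 0.50: (1.483 − 1.645 × 0.707)/√0.49 = 0.457, so power is 67.6%.

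| Discordance | Asymptotic power | Exact power | n for 90% (asymptotic) |
|---|---|---|---|
| 15% | 98.8% | 99.0% | 125 |
| 20% | 95.7% | 95.1% | 168 |
| 25% | 91.1% | 89.6% | 211 |
| 30% | 86.0% | 83.7% | 254 |
| 40% | 76.1% | 72.9% | 339 |
| 46% (no association, baseline 60%) | 70.8% | 67.5% | 391 |
| 50% (no association, baselines 40% and 50%) | 67.6% | 64.4% | 425 |

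Solving for 90% gives pd = 26.1% (asymptotic) or 24.7% (exact conditional test averaged over the number of discordant pairs).

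**Step 3: what the limit means.** The pre/post correlation is φ = [(p0 + p1 − pd)/2 − p0·p1] / √(p0(1 − p0)p1(1 − p1)). At pd = 0.261 and p0 = 0.50: (0.4195 − 0.300)/0.245 = 0.49. At p0 = 0.40 it is also 0.49, and at 0.60 it is 0.44. At p0 = 50%, the limit has (26.1 − 10)/2 = 8.05% of all patients losing MRD-negativity (16% of those negative) and 18.05% gaining it (36% of those positive).

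**Step 4: what the interim looks can resolve.** If 26% discordance is observed, the Wilson 95% interval is 15.9-39.6% at 13/50 (power 98.4% to 76.5%) and 19.6-33.6% at 39/150 (power 96.0% to 82.4%).

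**The case against.** The case for leaving the text alone has four parts.

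- **Disclosure and re-estimation.** Section 15.1 admits that the association is unknown and at once commits to an interim look with adjustment of the sample size. Section 15.4 adds a second look. The pre/post table used there contains the discordant cells. This stands as mitigation: a reader is told that 220 is provisional. It does not correct the 90%, because the plan never says that this figure depends on the association. It names neither discordance as the re-estimated quantity nor a decision rule.
- **High discordance is remote.** At a 50% baseline, 30%, 40% and 50% discordance mean that 20%, 30% and 40% of MRD-negative patients turn positive during four cycles of triplet therapy. Removal from study at progression (5.7) and the completers-only efficacy set (15.3) could lower discordance further. This stands too. The 76% and 68% figures mark the far end of the range and are not forecasts. At 30% discordance the shortfall is four points.
- **The hypothesised effect is larger.** Section 1.4.1 hypothesises at least a "15% improvement in MRD-negative rate". At 15 points, power is 93.8% (92.7% exact) even at 50% discordance. That is correct, but 15.1 attaches its 90% to the 10-point gain, which it sets as the smallest worth pursuing.
- **The formula is inferred.** Matching 90% does not prove that the one-sample formula was used. That is also correct. The point does not need it: the two-independent-samples reading, which would be conservative under positive association, does not give 90% at 220.

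**Conclusion.** The concern holds. With 220 evaluable patients, a 10-point gain and 1-sided 0.05, the planned McNemar test has 90% power only if no more than about 26% of patients change MRD status (24.7% for the exact test), a pre/post correlation of at least about 0.44 to 0.49. With no association, power is 68-71%. The 90% is therefore conditional on a quantity the plan does not state, and the description of the sizing as conservative is unsupported.

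This is not evidence that the trial is underpowered. Discordance below 26% is plausible, in which case 220 is sufficient or more than sufficient. The result takes the favourable reading that the McNemar test is 1-sided, as in 15.1; a 2-sided 0.05 test would lower the limit to about 21%. The point should be fixed, because it concerns the stated power for the primary endpoint and costs only wording.

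**What to change.** Keep 220 and restate the power in 15.1, for example:

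> With the 1-sided 0.05 McNemar test, 220 evaluable patients give 90% power for a 10-point improvement if the discordant proportion is no more than about 26% (just under 25% for the exact test). Power is about 99%, 96%, 91%, 86%, 76% and 68% at 15%, 20%, 25%, 30%, 40% and 50% discordance; 46-50% corresponds to no pre/post association at baselines of 40-60%.

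Delete the description of the sizing as conservative. Alternatively, if a one-sample formula was used, name it and state that it treats the baseline rate as known.

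Two optional clarifications would help: repeat the sidedness and name the McNemar version in 15.3, and name observed discordance as an input to the re-estimation already planned in 15.4.

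The cost is wording in 15.1. The stated power becomes conditional and less favourable. The sample size, test and endpoint are unchanged, and no patients are added beyond what the planned re-estimation may call for.
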